9.3.4 Work Productivity

The Work Productivity and Activity Impairment Questionnaire: Specific Health Problem (WPAI:SHP) measures the work productivity and activity impairment, will be completed by the patients at baseline and at 4, 12 and 24 weeks.

9.3.5 Clinical Effectiveness

HiSCR is a clinical endpoint focusing on assessment of HS inflammatory signs and symptoms that will determine the clinical effectiveness of Adalimumab.

Assessment will be performed by the physician at baseline and at 4, 12 and 24 weeks. HiSCR requires:

- At least a 50% reduction in the total abscess and inflammatory nodule count (AN count) relative to baseline, and
- No increase in abscess count, and
- No increase in draining fistula count.

9.3.6 Safety Parameters

Please see section 11.0

9.4 Data Sources

Data will be collected from the patient's medical records, by investigator assessment and by patient questionnaires as described in section 9.1.1 Study Flow Chart and in Section 9.3 Variables.

Electronic Case Report Forms (eCRF) will be used for each patient enrolled in this study. These forms will be used to transmit information collected during the study to AbbVie

9.5 Study Size

With 50 evaluable patients, the power is 90% based on a change in DLQI of -5.4, and an assumed standard deviation of 11.5 and type I error of 5% (two-sided). The drop-out rate is considered to be low, approximately 5% after 12 weeks, which will have a minimal impact on the power (decreased to 88%).

9.6 Data Management

Source documents are defined as original documents, data and records. This may include hospital records, clinical and office charts, laboratory data/information and patients' questionnaires. Data collected during this study must be recorded on the appropriate source documents.

The following assessments that will be completed by the patients or physician will be considered source documentation:

- DLQI
- EQ-5D
- HSIA
- Patient's Global Assessment of Skin Pain (NRS)
- WPAI:SHP
- HiSCR

Electronic Case Report Forms (eCRF) must be completed for each patient enrolled in this study. These forms will be used to transmit information collected during the study to AbbVie.

The eCRF data for this study are being collected in a system called VieDoc® provided by the technology vendor Pharma Consulting Group, PCG.

The investigator will document patient data in his/her own patient files. These patient files will serve as source data for the study. Investigative site personnel will record all eCRF data required by this protocol in the eCRF system.

The investigator or an authorized member of the investigator's staff will make any necessary corrections to the eCRF. All change information, including the date and person

performing the corrections, will be available via the audit trail, which is part of the system.

For any correction, a reason for the alteration will be provided. The eCRFs will be reviewed periodically for completeness, legibility, and acceptability by AbbVie personnel (or their representatives). As applicable, AbbVie (or their representatives) will also be allowed access to all source documents pertinent to the study in order to verify eCRF entries. The Principal Investigator will review the eCRFs for completeness and accuracy and provide his or her electronic signature and date to eCRFs as evidence thereof.

PCG will provide access to the eCRF for the duration of the trial through a passwordprotected method of Internet access. Such access will be removed from investigator sites at the end of the site's participation in the study. Data from the eCRF system will be archived on appropriate data media (CD-ROM, etc.) and provided to the investigator at that time as a durable record of the site's eCRF data. It will be possible for the investigator to make paper printouts from that media.

9.7 Data Analysis

All statistical analyses will be performed at Scandinavian Development Services AB (SDS), Danderyd, Sweden using SAS® (Version 9.3 or higher, SAS Institute Inc., Cary, NC, USA).

Continuous variables will be summarized using descriptive statistics (n, mean, SD, min, Q1, median, Q3, max). Categorical variables will be summarized in frequency tables (frequency and proportion). Graphical presentations, e.g. describing the change over time, will be used as appropriate, and individual patient data will be listed.

The primary and secondary endpoints (change in DLQI, Patient's Global Assessment of Skin Pain (NRS), HSIA, HiSCR, EQ5D, WPAI:SHP at 4, 12 and 24 weeks) will be analyzed using t-test or non-parametric methods such as Wilcoxon signed rank test as appropriate. The change at 12 weeks will be of primary interest.

No adjustment for multiple comparisons will be made.

A more detailed Statistical Analysis Plan (SAP) will be written and finalized before database lock.

9.8 Quality Control

An investigator's meeting and/or study initiation visit will be organized by AbbVie personnel in order to train the investigator(s) and study coordinator(s) on the protocol, eCRF procedures and other study procedures.

The study will be monitored in accordance with the pre-defined Monitoring Plan. Source document review will be performed against entries in the eCRF database as applicable and a quality assurance check will be performed.

Computer logic and manual checks will be run to identify items such as inconsistent study dates. Any necessary corrections will be made to the eCRF.

A Study Designated Physician (SDP) at AbbVie will conduct a review of all collected Serious Adverse Events and spontaneously reported Adverse Events.

9.9 Limitations of the Research Methods

This is a Post Marketing Observational Study in which the outcome of the treatment will be compared to the baseline data for each individual patient, i.e. no control groups exist in the study.

9.10 Other Aspects

N/A

10.0 Protection of Human Subjects

10.1 Ethical Conduct of the Study

The study will be conducted in accordance with the ethical principles that have their origin in the Declaration of Helsinki, the protocol, Good Clinical Practice (GCP) as applicable and applicable Swedish regulations.

10.2 Independent Ethics Committee (IEC)

Good Clinical Practice (GCP) requires that the clinical protocol, any protocol amendments, the informed consent and all other forms of patient information related to the study (e.g., advertisements used to recruit subjects) and any other necessary documents be reviewed by an IEC. The IEC will review the ethical, scientific and medical appropriateness of the study before it is conducted. IEC/IRB approval of the protocol, informed consent and patient information and/or advertising, as relevant, will be obtained prior to the start of any study procedure.

Any amendments to the protocol will require IEC approval prior to implementation of any changes made to the study design. The investigator will be required to submit, maintain and archive study essential documents according to GCP.

Any Serious Adverse Events that meet the reporting criteria, as dictated by local regulations, will be reported to the Regulatory Agencies, as required by local regulations.

10.3 Patient Information and Consent

The investigator or his/her representative will explain the nature of the study to the patient, and answer all questions regarding this study. Prior to any study-related procedures being performed on the patient, the informed consent statement will be reviewed and signed and dated by the patient, the person who administered the informed consent, and any other signatories according to local requirements.

A copy of the informed consent form will be given to the patient. An entry must also be made in the patient's source documents to confirm that informed consent was obtained prior to any study-related procedures and that the patient received a signed copy.

11.0 Management and Reporting of Complaints

A Complaint is any written, electronic, or oral communication that alleges deficiencies related to the physical characteristics, identity, quality, purity, potency, durability, reliability, safety, effectiveness, or performance of a product/device after it is released for distribution.

The investigational product in this trial contains both:

- Biologic compound(s) and
- Device component(s) (pre-filled syringe, pen).

Complaints associated with any component of this investigational product must be reported to the Sponsor (Section 11.2.2). For adverse events, please refer to Sections 11.1.1 through 11.1.6. For product complaints, please refer to Section 11.2.

11.1 Medical Complaints

11.1.1 Adverse Event Definition and Serious Adverse Event Categories

An adverse event (AE) is defined as any untoward medical occurrence in a patient, which does not necessarily have a causal relationship with their treatment. An adverse event can therefore be any unfavorable and unintended sign (including an abnormal laboratory finding), symptom, or disease temporally associated with the use of a medicinal product, whether or not the event is considered causally related to the use of the product.

Such an event can result from use of the drug as stipulated in the labeling, as well as from accidental or intentional overdose, drug abuse, or drug withdrawal. Any worsening of a pre-existing condition or illness is considered an adverse event.

If an adverse event meets any of the following criteria, it is considered a serious adverse event (SAE):

Death of Patient:	An event that results in the death of a patient.		
Life-Threatening:	An event that, in the opinion of the investigator, would have resulted in immediate fatality if medical intervention had not been taken. This does not include an event that would have been fatal if it had occurred in a more severe form.		
Hospitalization:	An event that results in an admission to the hospital for any length of time. This does not include an emergency room visit or admission to an outpatient facility.		

Prolongation of Hospitalization: Congenital Anomaly:	An event that occurs while the study patient is hospitalized and prolongs the patient's hospital stay. An anomaly detected at or after birth, or any anomaly that results in fetal loss.	
Persistent or Significant Disability/Incapacity:	An event that results in a condition that substantially interferes with the activities of daily living of a study patient. Disability is not intended to include experiences of relatively minor medical significance such as headache, nausea, vomiting, diarrhea, influenza, and accidental trauma (e.g., sprained ankle).	
Important Medical Event Requiring Medical or Surgical Intervention to Prevent Serious Outcome:	An important medical event that may not be immediately life-threatening or result in death or hospitalization, but based on medical judgment may jeopardize the patient and may require medical or surgical intervention to prevent any of the outcomes listed above (i.e., death of patient, life threatening, hospitalization, prolongation of hospitalization, congenital anomaly, or persistent or significant disability/incapacity). Additionally, any elective or spontaneous abortion or stillbirth is considered an important medical event. Examples of such events include allergic bronchospasm requiring intensive treatment in an emergency room or at home, blood dyscrasias or convulsions that do not result in inpatient hospitalization, or the development of drug dependency or drug abuse.	

11.1.2 Severity

The following definitions will be used to rate the severity for any adverse event being collected as an endpoint/data point in the study and for all serious adverse events.

Mild: The adverse event is transient and easily tolerated by the patient.

abb∨ie	Adalimumab P15-692 Protocol	
Moderate:	The adverse event causes the patient discomfort and interrupts the patient's usual activities.	
Severe:	The adverse event causes considerable interference with the patient's usual activities and may be incapacitating or life threatening.	

11.1.3 Relationship to Pharmaceutical Product

The following definitions will be used to assess the relationship of the adverse event to the use of product:

Reasonable Possibility	An adverse event where there is evidence to suggest a causal relationship between the product and the adverse event.
No Reasonable Possibility	An adverse event where there is no evidence to suggest a causal relationship between the product and the adverse event.

If no reasonable possibility of being related to product is given, an alternate etiology must be provided for the adverse event.

11.1.4 Serious Adverse Event Collection Period

Serious adverse events will be reported to AbbVie from the time the physician obtains the patient's authorization to use and disclose information (or the patient's informed consent) until 30 days or 5 half-lives following the intake of the last dose of physician-prescribed treatment.

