9.1.1 Study Flow Chart

Patients that have been prescribed Adalimumab as per routine care will asked to participate in this study. In accordance with routine care, a patient will be seen by the patient's physician at baseline (inclusion) and approximately 4, 12 and 24 weeks after the first dose of Adalimumab.

Parameters	Baseline	Week	Week	Week
		4	12	24
Informed consent	Х			
Demographic/baseline data	Х			
Dermatology Life Quality Index (DLQI)	Х	Х	Х	Х
EuroQol (EQ-5D)	Х	Х	Х	Х
Patient's Global Assessment of Skin Pain (NRS)	Х	Х	Х	X
Work Productivity and Activity Impairment	Х	Х	Х	X
Questionnaire: Specific Health Problem				
(WPAI:SHP)				
Hidradenitis Suppurativa Impact Assessment	Х	Х	Х	Х
(HSIA)				
Hidradenitis Suppurativa Clinical Response	Х	Х	Х	Х
(HiSCR)				
Serious Adverse Event		Х	Х	X
Pregnancy Reporting		Х	Х	X
Concomitant Medication	Х	Х	Х	X
Surgical Treatment	Х	Х	Х	Х
Missed Adalimumab doses		Х	Х	X

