4.3 Effectiveness analysis sets

4.3.1 Full analysis Set (FAS), (modified Intention-to-treat(ITT)

The FAS will include all enrolled patients, with the exception of subjects who were enrolled and not treated with any dose of adalimumab, or who had no baseline or post baseline data collected for the primary endpoint Dermatology Life Quality Index (DLQI). In case all of a patients post baseline assessments of DLQI are outside visit windows, the patient is excluded from FAS.

The FAS will be used for baseline characteristics and analysis of effectiveness.

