4.4 Safety analysis set

The safety analysis set will include all subjects given at least one dose of adalimumab and for whom follow-up safety data are available. Subjects/data will be summarised and analysed according to the total dose dispensed.

The Safety analysis set will be used for analysis of safety endpoints.

5 Endpoints

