5.3 Safety endpoints

• Non-serious Adverse events

As the safety profile of Adalimumab is stable and well established, non-serious events will not be actively solicited as these events are not likely to further contribute

to the understanding of the safety profile of the product. Any non-serious reports will be collected as spontaneous reports if notified to AbbVie.

• Serious Adverse events

Serious adverse events will be reported to AbbVie from the time the physician obtains the patient's authorization to use and disclose information (or the patient's informed consent) until 30 days or 5 half-lives following the intake of the last dose of physician-prescribed treatment.

In the CRF the response to the following question is registered at 4, 12 and 24 week visits:

Has any SAE(s) occurred since last visit?

6 Analysis Methods

The final statistical analyses will be performed at Scandinavian Development Services AB, Danderyd, Sweden by using the SAS ® version 9.3 or higher.

Continuous variables will be summarized using descriptive statistics (n, mean, SD, min, median, max). Categorical variables will be summarized in frequency tables (frequency and proportion). Graphical presentations, e.g. describing the change over time, will be used as appropriate, and individual patient data will be listed.

The primary and secondary endpoints (change in DLQI, Patient's Global Assessment of Skin Pain (NRS), EQ-5D VAS score and WPAI:SHP at 4, 12 and 24 weeks) will be analyzed using paired samples t-tests or non-parametric methods such as Wilcoxon signed rank test as appropriate.

HiSCR is a dichotomous response variable which will be analysed descriptively presenting proportion HiSCR with binomial exact 95% confidence interval.

The change at 12 weeks will be of primary interest.

Visit windows regarding 4, 12 and 24 weeks assessments following first dose of Adalimumab will decide the validity of assessment.

•	Baseline	Last assessment before first dose of Adalimumab
•	4 weeks	Day $(4*7)$ - $(3*7) \ll 4$ weeks \ll Day $(4*7)$ + $(3*7)$

•	12 weeks	Day (12*7)-(4*7)	<= 12 weeks <= Day (12*7)+(4*7)
•	24 weeks	Day (24*7)-(7*7)	<= 24 weeks <= Day (24*7)+(7*7)

Assessments outside these visit windows will not be part of input for summaries by visit. Such assessments will only be presented in listings.

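### The SAE reporting period runs from consent to a limit after last dose, but the only planned SAE summary goes by visit to week 24 and does not separate pre-dose or late off-drug events

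*Protocol*

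**What the plan says.** **Reporting period.** Protocol 11.1.4 opens SAE reporting at consent or authorization and runs it "until 30 days or 5 half-lives following the intake of the last dose of physician-prescribed treatment". SAP 5.3 repeats this. Neither document gives a half-life or says which limit governs.

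**Collection.** The flow charts (protocol 9.1.1, SAP 3.1.1) place consent at baseline and SAE recording at weeks 4, 12 and 24, with visits timed "approximately 4, 12 and 24 weeks after the first dose of Adalimumab". The CRF question at those visits is "Has any SAE(s) occurred since last visit" (SAP 5.3). SAP section 6 defines baseline as "Last assessment before first dose of Adalimumab".

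**Analysis.** SAP 6.5 plans one thing: a descriptive summary of the answers to that question at the three visits. SAP 4.4 sets the population: "The safety analysis set will include all subjects given at least one dose of adalimumab", provided follow-up safety data exist. It adds that data will be analysed by total dose dispensed. Protocol 9.1 says the sponsor does not supply the drug.

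**Dates.** Protocol 9.3.1 lists the adalimumab start date and missed doses. It does not list a last-dose date.

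**The concern.** The reporting period is defined by consent and last dose, whereas the summary is defined by visits. Nothing in the SAP translates one into the other, and neither document defines a treatment-emergent or on-treatment SAE. Three kinds of event are affected:

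- **Before first dose.** The safety set removes patients who were never dosed. It does not remove pre-dose events in patients dosed later, and those fall inside the look-back of the week 4 question.
- **Long after an early stop.** The question covers all time since the previous visit, so an off-drug event is pooled with events on drug.
- **After the week 24 visit.** The event may still be reportable, but no table or summary is planned for it.

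A reader of the study report would take the by-visit figures as SAEs on adalimumab. With one arm, no comparison would reveal the misplacement.

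**Working it through.** The plan gives no SAE figure to reproduce. The check is a comparison of the texts plus day arithmetic, with days counted from first dose.

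**Inputs from the documents:** planned visits on days 28, 84 and 168, and a week 24 window of 168 ± 49, i.e. day 119 to day 217 (SAP section 6); the 30-day limit (protocol 11.1.4); 50 evaluable patients (protocol 9.5).

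**Assumed, because the documents are silent:** gap g from consent to first dose of 7, 14 or 28 days; half-life h of 7, 10, 14 or 20 days; patients who stop early still attend later visits.

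**1. Can a pre-dose event enter the summary?** Consent is at baseline, and baseline precedes first dose. SAP 4.3.1 foresees "subjects who were enrolled and not treated with any dose of adalimumab", so enrolment does not wait for dosing. The week 4 question looks back to baseline. A pre-dose SAE in a patient treated later is therefore a yes at week 4.
- Pre-dose share of the week 4 look-back, g/(g+28): 7/35 = 20%; 14/42 = 33%; 28/56 = 50%.
- Pre-dose share of the time to week 24, g/(g+168): 7/175 = 4%; 14/182 = 8%; 28/196 = 14%.

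These are shares of time, not of events.

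**2. Early stop, visits held on the planned days.**
- Last dose day 28, 30-day limit: the window closes on day 58, and the answers reach 168 − 58 = 110 days beyond it. Of these, 84 − 58 = 26 days fall in the week 12 answer and 168 − 84 = 84 in the week 24 answer.
- Last dose day 84, 30-day limit: the window closes on day 114, leaving 168 − 114 = 54 days, all in the week 24 answer.
- With 5h instead (35 to 100 days): a day 28 stop closes on day 63 to 128, leaving 105 to 40 days. A day 84 stop closes on day 119 to 184, leaving 49 to 0 days.

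**3. After week 24.** With a last dose on day 168, the period ends on day 168 + 30 = 198, or on day 168 + 5h = 203, 218, 238 or 268. If the week 24 visit is on day 168, 30 to 100 days of reporting have no planned summary. For a patient still on drug, the text gives no closing day.

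**4. The two limits.** They agree only if 5h = 30, i.e. h = 6 days. Otherwise they differ by 5h − 30 = 5, 20, 40 or 70 days.

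**5. Scale.** One patient in 50 is 1/50 = 2 percentage points.

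**The case against.** The strongest reply is that 11.1.4 is a rule for reporting to the sponsor, not an analysis definition. Starting at consent is not a fault. SAP 6.5 never calls the events on-treatment. Each SAE gets a causality assessment (protocol 11.1.3) and sponsor physician review (9.8), and individual data are listed. All of that stands and limits the harm. It does not supply a rule separating pre-dose or late off-drug events in the one planned summary.

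A reader might also infer several stronger points that the documents do not support:

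- **That SAE counts are tied to exposure at neither end.** Protocol 11.1.4 does tie the end to the last dose. It is the summary that is not so tied.
- **That most patients will still be on drug at week 24.** This is plausible in routine care, but no continuation rate is given.
- **That the unresolved choice of limit changes the reported result.** The question covers all time since the last visit, and the summary closes at the week 24 visit under either reading. The ambiguity mainly affects reporting to the sponsor.
- **That late SAEs have no route in.** Protocol 9.6 says of eCRF access: "Such access will be removed from investigator sites at the end of the site's participation in the study". That is per site, not per patient. Section 11.1.5 requires notification within 24 hours of awareness, with fax or e-mail as backup.
- **That no last-dose date is recorded.** The flow chart and variable list omit it, but the eCRF is not among the documents.

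**Conclusion.** The point holds as a mismatch between an exposure-based reporting period and a visit-based summary. The route by which pre-dose events reach week 4 follows directly from the text. The pooling of late off-drug events also follows, provided patients who stop early keep attending. Reported SAEs after the week 24 visit have no planned summary.

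The size is uncertain. The consent-to-dose gap and the half-life are assumptions, and no expected number of SAEs is given, so the shares of time cannot be turned into event counts. Safety here is descriptive, single-arm and in about 50 patients; the stated objectives include no safety objective; and the DLQI analysis is untouched. Severity is minor, but the correction costs almost nothing.

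**What to change.** Amend SAP 6.5 to tabulate SAEs by onset date:

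- before first dose, using the start date already collected;
- on or after first dose and within the protocol's reporting window after last dose;
- after the recorded last dose plus that window;
- after the week 24 visit.

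State which category takes precedence when an event fits two, so that each is counted once. The third category matters: calling everything from first dose onward on-treatment would have no upper bound for a patient who stopped early. The by-visit summary can stay alongside.

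The sponsor should also reconcile protocol 11.1.4 and SAP 5.3 with both flow charts and SAP 6.5, so that one end of collection applies at all sites and the closing point for patients still on drug is stated. The sponsor should confirm that the eCRF holds an SAE onset date and a last-dose date or an entry for ongoing treatment. The total-dose-dispensed wording in SAP 4.4 should be removed or tied to data that are actually collected.

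The cost is wording, one derived flag and possibly one eCRF field.
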